5.0 Consent Process and Documentation

Refer to the following materials:

- The "HRP-090- SOP - Informed Consent Process for Research" outlines the process for obtaining informed consent.
- The "HRP-091- SOP - Written Documentation of Consent" describes how the consent process will be documented.

- The “HRP-314- Worksheet - Criteria for Approval” section 7 lists the required elements of consent.
- The “HRP-312- Worksheet - Exemption Determination” includes information on requirements for the consent process for exempt research. In addition, the CATS IRB Library contains consent guidance and templates for exempt research.
- The CATS IRB library contains various consent templates for expedited or full review research that are designed to include the required information.
- Add the consent document(s) to your study in CATS IRB (<http://irb.psu.edu>). Links to Penn State’s consent templates are available in the same location where they are uploaded. DO NOT include the actual consent wording in this protocol.

[Do not type here]

5.1 Consent Process:

Check all applicable boxes below:

Informed consent will be sought and documented with a written consent form [Complete Sections 5.2 and 5.6; If this is the only box checked, mark Sections 5.3, 5.4 and 5.5 as 'Not applicable']

Implied or verbal consent will be obtained – subjects will not sign a consent form (waiver of written documentation of consent) [Complete Sections 5.2, 5.3 and 5.6; If this is the only box checked, mark Sections 5.4 and 5.5 as 'Not applicable']

Informed consent will be sought but some of the elements of informed consent will be omitted or altered (e.g., deception). [Complete section 5.2, 5.4 and 5.6; If this is the only box checked, mark Section 5.5 as 'Not applicable']

Informed consent will not be obtained – request to completely waive the informed consent requirement. [Complete Section 5.5; If this is the only box checked, mark Sections 5.2, 5.3, 5.4 and 5.6 as 'Not applicable']

5.2 Obtaining Informed Consent

5.2.1 Consent Process

Describe the consent process, including when and where it will take place.

Aims 1 and 2: Residents

For each resident who is potentially eligible, the informed consent process will begin prior to research team's screening (screening steps 2 and 3).

Prior to consenting, the research team will assess the resident's capacity to consent for research. All potentially eligible resident participants will be approached to assess their capability of providing consent using the Evaluation to Sign Consent (ESC). The ESC is a five-item measure and its psychometrics have been established in assessing older adult's capacity to consent for research (Resnick et al., 2007). The details of this assessment instrument are provided in section 5.6.2.1. Based on the assessment, if the resident is determined to be capable of consenting, the research team will proceed with the informed consent process with the resident. Resident consent will be conducted in-person and will take place at the facility. We will meet with the resident at the nursing home facility and explain the study to the resident using the consent form. If the resident agrees to participate, we will ask him/her to sign the consent forms in-person.

For residents who are not capable of consenting and/or have a LAR, we will contact the LAR to provide consent for the resident after completing the first two steps of screening.

To obtain informed consent from the LAR, the study team will conduct the following protocol. First, the research team will obtain the LAR's name and contact information from nursing home staff under the residents' permission or directly from the LAR. Second, we will consent the LAR in-person or remotely via phone. In-person consent will take place either at the facility, our research office, or location of their choice with privacy. For in-person consent, we will ask the LAR to sign the consent forms in-person. For remote consent, we will ask the LAR to sign the consent forms, scan the forms, and then either send back the signed consent forms either via mail, email, or in person.

Aim 3: Staff and administrators

We will provide staff and administrators the consent forms in person or via mail or email and obtain their consent in person or remotely via phone or videoconference (e.g., zoom). In-person consent will take place either at the facility, our research office, or location of their choice with privacy and will ask them to sign the consent forms in-person.

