Participants will be recruited as soon as we have IRB approval and permission from nursing homes.

4.2.4 Describe the eligibility screening process. Screening begins when the investigator obtains information about or from a prospective participant in order to determine their eligibility.

- Eligibility screening is occurring *before* consent* - describe the process below
- Eligibility screening is occurring *after* consent - describe the process below
- Eligibility screening is occurring, consent is not being obtained in this research - describe the process below
- Not applicable - Eligibility screening is not being done in this research

Aims 1 and 2: Residents

The screening process for residents involves three steps: 1) initial screening conducted by nursing home staff, 2) chart reviews conducted by the research team, and 3) interviews with primary staff/caregivers conducted by the research team. The step 1 screening will be conducted prior to the consent, and the steps 2 and 3 will be conducted after consent.

For step 1, the nursing home staff will conduct an initial screening based on our broad inclusion criteria: 1) age ≥ 55 , 2) English speaking, 3) long-term stay at the facility for at least 3 months, and 4) diagnosis of dementia.

For step 2, after the informed consent is obtained from LAR or resident as appropriate, the research team will review the residents' medical records to verify their eligibility based on the inclusion and exclusion criteria.

If the resident is not capable to consent and does not have a LAR to provide consent, they will not be eligible to participate in the study.

For residents who pass the step 2 screening, the research team will proceed with the screening and conduct additional assessments to confirm the presence of dementia and agitation. Specifically, the research team will assess residents' cognitive function by interviewing the residents and assess the residents' agitation symptoms based on inputs from the primary staff caregivers, which includes but is not limited to certified nurse assistants (CNAs), licensed practical nurses (LPNs), and registered nurse (RNs).

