5.6.2.1 Capability of Providing Consent

Describe the process to determine whether an individual is capable of consent.

All potentially eligible resident participants will be approached to assess their capability of providing consent using the Evaluation to Sign Consent (ESC). The ESC is a five-item measure and its psychometrics have been established in assessing older adult's capacity to consent for research (Resnick et al., 2007). The first item evaluates whether the individual is alert and able to communicate. The other four items assess the individual's understanding of the research study, including naming at least two potential risks incurred as a result of participating in the study, naming two things that will be expected of them related to participation, explaining what he/she could do if no longer interested in participating in the study, and what he/she could do if any distress or discomfort was experienced associated with study participation. Evidence of ability to sign consent is based on correct responses to all five items on the ESC.

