5.6.2.3 Assent of Adults Unable to Consent

Describe the process for assent of the subjects. Indicate whether assent will be required of all, some, or none of the subjects. If some, indicate which subjects will be required to assent and which will not.

If assent will not be obtained from some or all subjects, provide an explanation of why not.

Describe whether assent of the subjects will be documented and the process to document assent. The IRB allows the person obtaining assent to document assent on the consent document and does not routinely require assent documents and does not routinely require subjects to sign assent documents.

Affirmative assent will not be obtained for this study. In my experience, when people with dementia are not capable of providing consent, that usually means that their cognitive function is too impaired to have a good understanding of the research (e.g., purposes and procedures). In that case, they would not be able to provide a meaningful assent either. Thus, in this study, when the residents cannot provide consent, we will not ask for their assent.

Alternatively, when we interact with them and conduct research procedures, such as asking questions for cognitive assessment and putting on the lighting monitor, we will ask their permission and observe their verbal response and non-verbal behavioral cues. When the resident verbally agrees or does not show observable resistance for the monitor. If they express observable verbal or non-verbal resistance to the procedures, such as stating "go away" "I don't want that" or push away the monitor, we will not proceed with the procedures and may approach the resident at a later time.

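### As written, Protocol 5.2.1 tests a resident's capacity to consent before the study is explained, although at least two of the five test items need that explanation

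*Protocol*

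**What the plan says.** The relevant text is spread over several sections of the Protocol.

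- **Timing of the test (5.2.1).** "Prior to consenting, the research team will assess the resident's capacity to consent for research". The instrument is the ESC.
- **What a pass leads to (5.2.1).** "Based on the assessment, if the resident is determined to be capable of consenting, the research team will proceed with the informed consent process". The section then describes that process: "We will meet with the resident at the nursing home facility and explain the study to the resident using the consent form", followed by signature if the resident agrees.
- **What the test asks (5.6.2.1).** The first item is alertness and ability to communicate. "The other four items assess the individual's understanding of the research study, including naming at least two potential risks incurred". The remaining three cover two things the study will expect of the person, what to do if they no longer want to take part, and what to do if distressed.
- **Pass mark (5.6.2.1).** "Evidence of ability to sign consent is based on correct responses to all five items on the ESC".
- **After a fail.** The LAR is asked to sign on the resident's behalf (5.6.2.2). On assent: "Thus, in this study, when the residents cannot provide consent, we will not ask for their assent" (5.6.2.3, Assent of Adults Unable to Consent). Where there is no LAR: "If the resident is not capable to consent and does not have a LAR to provide consent, they will not be eligible" to take part (4.2.4).

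**The concern.** A test of whether someone understands a study can only be scored fairly once that person has been told about it. In the order that 5.2.1 sets out, the telling comes after the test and is reserved for those who pass. A wrong answer on the study-specific items may then mean that the resident lacks capacity, or only that nobody has yet described the study, and the score cannot show which.

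This matters because three later rules depend on the result: who signs, whether assent is sought, and whether a resident without a LAR can take part at all. The Protocol's reason for not seeking assent is that people who cannot consent are usually too impaired to understand the research. That reason does not apply to someone who failed because nothing had been explained. The Protocol plainly expects some residents to have capacity, since 5.2.1 and 5.6.2.2 both set out a path for them. The stated order undermines that path.

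**Working it through.** The Protocol gives no figure to reproduce here. The check is to trace the steps as written and count the ESC items that can be answered at each point.

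**1. Order of steps in 5.2.1.** ESC, then (if passed) the consent process, then within it the explanation with the consent form, then signature. The section opens by saying that the consent process starts before the research team's own screening. That places consent relative to screening steps 2 and 3. It does not place the explanation ahead of the ESC.

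**2. Is the resident told about the study earlier?** Section 4.2.1 lists three sources of information:
- a recruitment letter, sent to the family or LAR;
- recruitment meetings, held with family;
- flyers posted in the facility, which invite the family or LAR to make contact.

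A resident might see a flyer, but none of the three is described as an explanation to the resident. Section 5.2.2 says that voluntariness and the freedom to withdraw are conveyed while the study is being explained, so this too comes after the ESC in the stated order.

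**3. Which items need the explanation?**

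| ESC item (5.6.2.1) | Answerable without an explanation? |
|---|---|
| Alert and able to communicate | Yes |
| Two risks of this study | No |
| Two things expected of the participant | No |
| What to do if no longer interested | Possibly, with a general answer such as telling staff |
| What to do if distressed | Possibly, in the same way |

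**4. Best attainable score.**
- Only the risk and expectation items need the explanation: 5 − 2 = 3 of 5.
- The withdrawal and distress items need it as well: 5 − 4 = 1 of 5.
- Required: 5 of 5.

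Both scores fall short of the pass mark, so the conclusion does not depend on how the two doubtful items are classified.

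**5. Consequences of such a fail.**
- *A LAR is available.* The LAR consents (5.6.2.2) and assent is not sought (5.6.2.3). The same subsection keeps a partial safeguard: permission is asked at each procedure, and visible verbal or non-verbal resistance stops that procedure.
- *A documented LAR and true capacity.* Section 5.6.2.2 requires the LAR's consent in any case. A false fail does not bring the LAR in; it costs the resident their own consent.
- *No LAR.* The resident is ineligible (4.2.4).

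**The case against.** The strongest reply is that this is loosely ordered prose and not an instruction to test uninformed people. A test of understanding presupposes that the study has been described. Consenting could mean the act of signing. All potentially eligible residents are to be approached for the ESC, and staff may well describe the study at that point. The Protocol template also tells authors to keep consent wording and data-collection materials out of the document, so an ESC form or script showing the right sequence could exist elsewhere.

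Part of this stands. The documents do not show that any capable resident will in fact fail, and sensible staff may explain first. But 5.2.1 does more than leave the order open: it makes the consent process conditional on the test result and puts the explanation inside that process. Neither 5.2.1 nor 5.6.2.1 states the other order. If explanation first is the intention, it should be written down.

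A reader might also infer several stronger things that the documents do not support:

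- *That four of the five items are unanswerable.* Only two clearly are. The withdrawal and distress items may be answered in general terms.
- *That a count of misclassified or excluded residents can be given.* The documents report neither the share of residents with capacity nor the share without a LAR, so any count would rest on assumptions with no anchor.
- *That recruitment is endangered.* Section 15.2 gives 160 × 70% = 112 and 240 × 65% = 156 residents with dementia, 268 in total if both homes are full. Section 8.1 expects to screen 80 to enroll 40. Not all 268 would meet the agitation criteria, but no shortage is shown.
- *That the sample loses its least impaired members.* Section 3.1 requires a dementia diagnosis, BIMS of 12 or less and MoCA of 22 or less for everyone, and nothing shows how capacity is distributed within that group.
- *That residents who fail have no say.* The permission-and-resistance rule in 5.6.2.3 is a real protection, though it does not replace the informed consent of a capable adult.

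**Conclusion.** The point holds as a defect in the stated sequence. Taken literally, 5.2.1 and 5.6.2.1 together produce a test that cannot tell incapacity from not having been informed, because at least two items cannot be answered from anything the Protocol says the resident has been told, and all five are needed to pass. Residents with capacity are liable to fail on that ground. They would then be enrolled on a LAR's consent without giving their own consent or assent, or be ineligible if they have no LAR.

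The conclusion rests on one assumption: that staff follow the order in 5.2.1 and nobody explains the study to the resident beforehand. The number affected cannot be estimated from the documents. No endpoint, analysis or power figure is shown to be affected. The point concerns the protection of a vulnerable population, and it is worth correcting because the correction is so cheap.

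**What to change.** Amend 5.2.1 and 5.6.2.1 so that both state the same order:

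1. The research team explains the study, using the consent form, to every potentially eligible resident.
2. The ESC is then given and scored.
3. A resident who passes and agrees signs, with the LAR's consent also obtained where 5.6.2.2 requires it. For a resident who does not pass, the LAR is approached.

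In 5.2.1, the opening phrase that times the capacity assessment should say that it takes place after the explanation and before signature. This correction needs no change to 4.2.4, 5.6.2.2 or 5.6.2.3; their rules would then act on a result obtained after the resident has been informed. If a separately filed script already has this order, the Protocol should be brought into line with it.

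The cost is a wording change in two sections and a few more minutes explaining the study to residents who then fail the ESC.

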5.2.2 Coercion or Undue Influence during Consent

Describe the steps that will be taken to minimize the possibility of coercion or undue influence in the consent process.

For consent of all research participants (i.e., the residents, staff, and administrators), in the course of explaining the study, all participants will be told that participation in this research study is totally voluntary, and they are free to withdraw at any time. The research team will emphasize to residents and family members that participation will not influence the quality of care the resident receives in any way. We will also emphasize to staff that their participation decision will in no way impact their job status or performance review.

5.3 Waiver of Written Documentation of Consent

Review "HRP – 411 – Checklist – Waiver of Written Documentation of Consent."

5.3.1 Indicate which of the following conditions applies to this research:

The research presents no more than minimal risk of harm to subjects and involves no procedures for which written consent is normally required outside of the research context.

OR

The only record linking the subject and the research would be the consent document and the principal risk would be potential harm resulting from a breach of confidentiality. Each subject will be asked whether the subject wants documentation linking the subject with the research, and the subject's wishes will govern. *(Note: This condition is not applicable for FDA-regulated research. If this category is chosen, include copies of a consent form and /or parental permission form for participants who want written documentation linking them to the research.)*

OR

If the subjects or legally authorized representatives are members of a distinct cultural group or community in which signing forms is not the norm, that the research presents no more than minimal risk of harm to subjects and provided there is an appropriate alternative mechanism for documenting that informed consent was obtained. *(Note: This condition is not applicable for FDA-regulated research.)*

For distinct cultural groups describe the alternative mechanism for documenting that informed consent was obtained:

Not applicable

5.3.2 Indicate what materials, if any, will be used to inform potential subjects about the research (e.g., a letter accompanying a questionnaire, verbal script, or implied consent form)

Not applicable

5.4 Informed consent will be sought but some of the elements of informed consent will be omitted or altered (e.g., deception).

Review "HRP-410-Checklist -Waiver or Alteration of Consent Process" to ensure that you have provided sufficient information.

5.4.1 Indicate the elements of informed consent to be omitted or altered

Not applicable

5.4.2 Indicate why the research could not practicably be carried out without the omission or alteration of consent elements

Not applicable

5.4.3 Describe why the research involves no more than minimal risk to subjects.

Not applicable

5.4.4 Describe why the alteration/omission will not adversely affect the rights and welfare of subjects.

Not applicable

5.4.25 If the research involves using identifiable private information or identifiable biospecimens, describe why the research could not practicably be carried out without using such information or biospecimens in an identifiable format.
Not applicable

5.4.26 Debriefing

Explain whether and how subjects will be debriefed after participation in the study. If subjects will not be debriefed, provide a justification for not doing so. Add any debriefing materials to the study in CATS IRB.

Not applicable

5.5 Informed consent will not be obtained – request to completely waive the informed consent requirement

Review “HRP-410-Checklist -Waiver or Alteration of Consent Process” to ensure that you have provided sufficient information.

5.5.1 Indicate why the research could not practicably be carried out without the waiver of consent

[Type protocol text here or indicate as not applicable]

5.5.2 Describe why the research involves no more than minimal risk to subjects.

[Type protocol text here or indicate as not applicable]

5.5.3 Describe why the alteration/omission will not adversely affect the rights and welfare of subjects.

[Type protocol text here or indicate as not applicable]

5.5.4 If the research involves using identifiable private information or identifiable biospecimens, describe why the research could not practicably be carried out without using such information or biospecimens in an identifiable format.

[Type protocol text here or indicate as not applicable]

5.5.5 Additional pertinent information after participation

Explain if subjects will be provided with additional pertinent information after participation.

Not applicable

5.6 Consent – Other Considerations

5.6.1 Non-English-Speaking Subjects

Indicate what language(s) other than English are understood by prospective subjects or representatives.

If subjects who do not speak English will be enrolled, describe the process to ensure that the oral and written information provided to those subjects will be in that language. Indicate the language that will be used by those obtaining consent.

Indicate whether the consent process will be documented in writing with the long form of the consent documentation or with the short form of the consent documentation. Review "HRP-091 -SOP- Written Documentation of Consent" and "HRP-103 -Investigator Manual" to ensure that you have provided sufficient information.

We do not plan to enroll participants who do not speak English at this time due to limited translation resources. We hope to expand the study population to non-English-speaking population in future research studies.

